8.4 Appropriateness of Assessments

The assessments used in this study conform to accepted standards for observational studies.

9. Safety Reporting

9.1 Adverse Events

This is an observational, noninterventional study assessing patients initiating treatment of XERMELO via web-based surveys. Given the indirect contact with patients, adverse event (AE) collection will be limited by the questions included in the survey.

Explorative objectives of CS-related hospitalizations and CS-related ER visits will be reported as AEs. All information will be captured as part of the web-based survey and will be reported to Sponsor using a format agreed by the Sponsor and RTI. Information related to these events will be patient reported, unless the event is designated by the Sponsor as requiring additional follow-up as described in [Section 9.4](#).

The AEs will be forwarded by the study team to the Sponsor within 24 hours of the completion of a survey using the following e-mail address.

E-mail address (in case of fax failure): [REDACTED]

Patient mortality will be collected outside of this study as part of routine practice at the specialty pharmacies and will be received by the Sponsor on an ongoing basis as spontaneous reports and reported as such. These data will be reported in this study only as the study endpoint.

In case where an AE is received outside of the web-based surveys by the study team, an AE Report form will be completed and sent to the Sponsor at the above e-mail address within 24 hours of the study team's awareness of the AE.

Exposure (either maternal or paternal) to XERMELO during pregnancy, received either through or outside the web-based surveys, will be reported following the same process as that for the AEs, and additional information will be collected following the process described in [Section 9.5.1](#).

9.2 Definition of an Adverse Event

An AE is defined as any untoward medical occurrence associated with the use of a drug in humans, whether or not considered drug related.

An AE includes any noxious, pathological, or unintended change in anatomical, physiological, or metabolic functions as indicated by physical signs or symptoms occurring in any phase of the clinical study whether or not considered related to the study medication. This definition includes an exacerbation of preexisting medical conditions or events, historical condition not present prior to study treatment, which reappear following study treatment, intercurrent illnesses, hypersensitivity reactions, drug interaction, or the significant worsening of the disease under investigation. Anticipated day-to-day fluctuations of preexisting conditions that do not represent a clinically significant exacerbation or worsening need not be considered AEs.

Medication error, overdose, misuse/abuse, and off-label use should also be reported and followed according to the same timeline and process as those for AEs.

9.3 Assessment of Adverse Events

The Sponsor will be responsible for assessing AEs collected for seriousness, expectedness, and causality using standard definitions and categories for safety reporting purpose.

9.4 Follow-up of Adverse Events

For events designated by the Sponsor as requiring additional information, consent will be obtained from the patient for additional contact and access to medical records as applicable. The follow-up action will be directed by the Sponsor and carried out by the study team and/or site staff. All actions will be in accordance with local and/or federal reporting requirements.

9.5 Special Situations

9.5.1 Pregnancy

Exposure of an embryo or infant to study medication during pregnancy or lactation (ie, in utero through either maternal exposure or transmission via semen following paternal exposure, or after birth via breast milk) should be reported and followed for the outcome of the pregnancy and/or development of the child, following the same timeline and process as those for AEs; see [Section 9.1](#) for contact information. The outcome of the pregnancy and the presence or absence of a congenital abnormality will be documented by completion of a Pregnancy Questionnaire and a Pregnancy Outcome Form in accordance with Good Clinical Practice (GCP) and International Council for Harmonisation (ICH) guidelines and the Sponsor's SOPs. Patients should report if they become pregnant or father a child within 30 days after last dose of XERMELO.

10. Statistical Methodology

10.1 Determination of Sample Size

The sample size was derived by satisfying design assumptions for the primary study endpoint of proportion of CS patients who are satisfied with their overall symptom control, 6 months after initiating treatment with telotristat ethyl (XERMELO). Of specific interest is the proportion of patients with CS who are at least somewhat satisfied with their control of CS at 6 months, defined as those patients with a response of either “very satisfied” or “somewhat satisfied”. [REDACTED] where [REDACTED]

[REDACTED] Two-sided 95% confidence limits (CLs) will be calculated for this proportion using normal approximation. [REDACTED]

[REDACTED] hen a minimum of N=643 patients with CS,

who initiate treatment with XERMELO, should be entered into the study. **Table 10.1-1** shows precision estimates with the expected 95% confidence intervals (CIs) assuming various combinations of sample size.

Table 10.1-1: Expected 95% Confidence Intervals

Sample size	Estimated proportion	Sides on CI	LCL (Exact)	UCL (Exact)	Width of exact interval	LCL (Wald)	UCL (Wald)	Width of Wald interval
[REDACTED]	[REDACTED]	[REDACTED]	[REDACTED]	[REDACTED]	[REDACTED]	[REDACTED]	[REDACTED]	[REDACTED]
[REDACTED]	[REDACTED]	[REDACTED]	[REDACTED]	[REDACTED]	[REDACTED]	[REDACTED]	[REDACTED]	[REDACTED]
[REDACTED]	[REDACTED]	[REDACTED]	[REDACTED]	[REDACTED]	[REDACTED]	[REDACTED]	[REDACTED]	[REDACTED]
[REDACTED]	[REDACTED]	[REDACTED]	[REDACTED]	[REDACTED]	[REDACTED]	[REDACTED]	[REDACTED]	[REDACTED]
[REDACTED]	[REDACTED]	[REDACTED]	[REDACTED]	[REDACTED]	[REDACTED]	[REDACTED]	[REDACTED]	[REDACTED]
[REDACTED]	[REDACTED]	[REDACTED]	[REDACTED]	[REDACTED]	[REDACTED]	[REDACTED]	[REDACTED]	[REDACTED]
[REDACTED]	[REDACTED]	[REDACTED]	[REDACTED]	[REDACTED]	[REDACTED]	[REDACTED]	[REDACTED]	[REDACTED]
[REDACTED]	[REDACTED]	[REDACTED]	[REDACTED]	[REDACTED]	[REDACTED]	[REDACTED]	[REDACTED]	[REDACTED]
[REDACTED]	[REDACTED]	[REDACTED]	[REDACTED]	[REDACTED]	[REDACTED]	[REDACTED]	[REDACTED]	[REDACTED]
[REDACTED]	[REDACTED]	[REDACTED]	[REDACTED]	[REDACTED]	[REDACTED]	[REDACTED]	[REDACTED]	[REDACTED]
[REDACTED]	[REDACTED]	[REDACTED]	[REDACTED]	[REDACTED]	[REDACTED]	[REDACTED]	[REDACTED]	[REDACTED]
[REDACTED]	[REDACTED]	[REDACTED]	[REDACTED]	[REDACTED]	[REDACTED]	[REDACTED]	[REDACTED]	[REDACTED]

10.2 Analysis Populations

The analysis population is comprised of all patients who provide consent, are enrolled into the study, and have data available for 1 or more of the primary and secondary endpoints.

10.3 Study Endpoints

10.3.1 Primary and Secondary Endpoints

The primary study endpoint is the proportion of CS patients who are satisfied with their overall symptom control, 6 months after initiation of treatment with telotristat ethyl (XERMELO).

Secondary endpoints include the following outcomes, assessed at 6 months among patients with CS after initiation of treatment with telotristat ethyl (XERMELO):

- Proportion of patients reporting satisfaction of CS-related diarrhea control
- Proportion of patients reporting satisfaction of CS-related flushing control

- Proportion of patients reporting reduction in rescue SSA use
- Proportion of patients reporting reduction in the dose of long-acting SSA injection
- Proportion of patients reporting reduction in the frequency of long-acting SSA injection
- Proportion of patients reporting an overall improvement in CS control after initiating XERMELO based on PGIC
- Proportion of patients that had improvement reduction in work-related absenteeism, presenteeism activity impairment, and overall productivity loss after initiating XERMELO based on WPAI- SHP
- Proportion of patients reporting weight gain

10.3.2 Other Endpoints

Other endpoints include incidence of CS-related hospitalizations, incidence of CS-related ER visits, and incidence of mortality at 6-month intervals for up to 3 years after initiation of treatment with XERMELO.

10.4 Statistical Methods

Descriptive statistics will be used to summarize the data. Continuous and ordinal variables will be summarized by n, mean, standard deviation, median, minimum, and maximum values. Categorical variables will be summarized by patient counts and related percentages. Summaries will be by study time point, as applicable.

Confidence limits corresponding to point estimates of the proportions or means corresponding to the study endpoints will be 2-sided and calculated with 95% confidence coefficient. Statistical tests will be 2-sided and have an associated α -level=0.05. As there is no specified hierarchy for the statistical tests and a potentially large number of tests may be performed without adjustments for multiplicity, the p-values from these tests will be considered descriptive rather than inferential.

All data will be provided in by-patient listings.

A more detailed description of the analysis and reporting of data will be provided in a Statistical Analysis Plan (SAP). An overview of the main analysis strategy is provided in the following sections.

10.4.1 Analyses of Study Endpoints

For the primary endpoint, the proportion of CS patients who are at least somewhat satisfied with their overall symptom control at 6 months, a point estimate and the corresponding 95% CLs will be calculated. Secondarily, a point estimate and corresponding 95% CLs will be calculated for the proportion of CS patients who are very satisfied with their overall symptom control at 6 months. The 95% CLs will be unadjusted and based on the assumption of approximate normal distribution. Missing data will not be imputed in the main analysis of the primary endpoint. As a sensitivity analysis, a patient with a missing response at 6 months will be imputed as a non-responder. This approach corresponds to non-responder imputation.

In addition to the point estimates and 95% CLs for the primary endpoint, the frequency distribution of the categorical responses, on a 5-point Likert scale, to patient satisfaction with overall symptom control at 6 months will be presented. The patient satisfaction measure will also be summarized as an ordinal variable with a value of 1 corresponding to “very dissatisfied” up to 5 corresponding to “very satisfied”.

All the secondary endpoints correspond to proportions and will be summarized through point estimates and 95% CLs, as described above for the primary endpoint. Frequency distributions of the categorical responses and summary statistics of the corresponding ordinal values of the categories will be presented. The handling of patients with a response of “not applicable” to patient satisfaction with CS-related diarrhea control or patient satisfaction with CS-related flushing control in the analysis will be described in the SAP.

The 4 WPAI-SHP scores at Baseline and month 6 will be summarized, as well as the change from Baseline to month 6.

The incidences of at least 1 CS-related hospitalization, at least 1 CS-related ER visit, and mortality after Baseline will be calculated at each 6-month interval. Kaplan-Meier estimates of each time-to-event variable, including quartiles, medians, and their corresponding 95% CLs, will be presented. The association or relationship between the primary endpoint and each long-term health outcome will be evaluated through descriptive statistics and the use of statistical models, as appropriate. Any statistical models that will be used and the appropriateness and/or limitations of their use will be described in the SAP.

For any other study endpoints assessed at 12 months and thereafter, descriptive statistics will be presented and 95% CLs will be calculated.

Subgroup analyses of study endpoints based on categories of sociodemographics or clinical characteristics of patients may be performed, but will serve as exploratory assessments only.

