3.2 Rationale for Current Study

This observational study will capture patient experience with XERMELO in a real-world setting. XERMELO is the first orally available drug to be indicated for the treatment of CS diarrhea.

The clinical development program provided experience in more than 200 patients with CS and demonstrated statistically significant reductions in daily BM frequency, as well as an acceptable safety and tolerability profile. Data from 2 clinical studies, TELESTAR and TELECAST, support that the mechanism of action for XERMELO holds an important role in the treatment of CS. By reducing the production of peripheral serotonin, XERMELO is able to significantly reduce the frequency of CS diarrhea.

Patient satisfaction with XERMELO was not thoroughly studied in the clinical program and is not readily available in medical records. Results of a 35-patient interview sub-study conducted in TELESTAR after 12 weeks of blinded treatment indicated that nearly all patients reporting reductions in BM frequency during the Double-blind Treatment Period described them as meaningful, allowing them to better enjoy life and participate more in social and physical activities. Among interview participants (n=33) answering the question about satisfaction with the ability of the blinded study drug to treat CS, 50% of patients (12/24) on active treatment reported “very satisfied” while 0 patients in the placebo group reported the same term. The Sponsor assumes that satisfied patients will continue XERMELO to avoid the complications of CS, leading to better long-term outcomes ([Lexicon Pharmaceuticals, Inc., Clinical Study Report, 2017](#)).

Real-world experience with pharmaceutical products may only be evaluated once the product is available within the marketplace. In capturing patient experience, this study will also assess the patient journey though medical diagnosis of NET and treatment for CS in the clinical setting.

4. Study Objectives

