If the study team is unsuccessful in reaching the patient, the patient will be considered lost-to-follow up and the study team will update the enrollment status as appropriate.

Upon completion of the electronic consent and successful enrollment, the patient will be prompted to complete an online survey at Baseline, then every 6 months for a period of up to 3 years. All surveys will be completed online, at the patient's convenience, and in accordance with [Appendix A](#). The study team will provide technical support and reminder prompts, as described above, throughout the duration of participation.

At any time after Baseline, if the study team is unable to reach a patient after 3 attempts and the patient does not complete the survey within the prespecified window, the patient will be considered lost-to-follow up and the study team will disable the patient's unique study link as appropriate. Awareness by the specialty pharmacy of any change in the patient's status (ie, withdrawal of consent, treatment discontinuation) must be communicated to the study team. Should the specialty pharmacy communicate a patient's status change during the 3-year Follow-up Period, the study team will disable the patient's unique study link upon notification and no further survey invitations or reminders will be triggered.

Information regarding a patient's initial prescription and refill(s) will also be collected from the specialty pharmacies for all enrolled patients.

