5.1.1 Survey Conduct

An electronic consent and survey questionnaire approved by an Institutional Review Board (IRB) will be used by RTI to program the online survey for the purpose of standardizing responses among patients.

Each patient will complete up to 7 web-based surveys over the duration of the study. Each survey is anticipated to take no more than 20 minutes on average.

All assessments, except mortality, will be patient-reported; medical records will not routinely be requested or reviewed as part of this observational study unless required for safety reporting purposes. As patient recall over time may be limited, partial responses as in the case of dates of onset, and/or estimates of numerical information will be accepted.

Participation in the study is contingent on continued use of XERMELO. Each survey will establish ongoing treatment with XERMELO and continued consent to study participation prior to subsequent data collection.

The initial survey is intended to gather Baseline information, which may include:

- Sociodemographics (age, year of birth, sex, race, ethnicity, education, geographic region)
- Current medical history as it relates to CS, NET burden, NET location, and related conditions
 - Location of NET
 - Date of diagnosis; CS and NET
 - CS-related hospitalization(s)
 - CS-related ER visit(s)
 - NET-related surgery (eg, tumor debulking, lysis of adhesions)
- Satisfaction with CS, CS-related diarrhea and/or flushing control prior to starting XERMELO, where applicable
- Height and weight
- Concomitant medication as it relates to the following:
 - Long-acting SSA therapy

- Use of rescue medication - short-acting SSA
- Systemic tumor-directed therapy
- Liver-directed therapy (eg, chemoembolization)
- WPAI-SHP

The initial survey should be completed no later than 30 days, and subsequent surveys should be completed no later than 14 days, after the unique survey link has been provided to the patient via e-mail. Patients will be asked to complete a survey every 6 months for up to 3 years. The following patient-reported data may be collected as described in [Appendix A](#):

- Satisfaction with CS, CS-related diarrhea and/or flushing control after initiating XERMELO, where applicable
- PGIC
- Concomitant medication as it relates to the following:
 - Change in use of rescue medication - short-acting SSA
 - Change in long-acting SSA therapy
 - Systemic tumor-directed therapy
 - Liver-directed therapy (eg, chemoembolization)

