8.2.1.2 Rescue Short-Acting Somatostatin Analogs (SSAs) and Long-acting SSAs

Beginning with the month 6 survey, patients will be asked to describe changes (ie, frequency, dosage) in the use of short and long-acting SSA therapy, where applicable, since initiating XERMELO.

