3.2.5 Work Productivity and Activity Impairment Questionnaire—Specific Health Problem (WPAI-SHP)

The WPAI-SHP is a self-administered questionnaire ([Reilly et al., 1993](#)) comprising 6 questions that measure the effect of health problems on participants' ability to work and participate in regular activities based on their experiences in the previous 7 days. This questionnaire will be administered at Baseline and at the initial 6-month Follow-up.

The WPAI-SHP includes 4 domains (absenteeism, presenteeism, work productivity loss, and activity impairment). All participants will be asked whether they are employed (Q1) and how their CS-related problems affected their regular activities (Q6). Employed participants will be asked about hours of work missed due to CS-related problems (Q2), hours of work missed for any reason (eg, vacation, holidays, time off to participate in this study) (Q3), hours actually worked (Q4), and the degree that CS affected their productivity while working (Q5). An integer scale from 0 to 10 is used for Q5 and Q6, where 0 corresponds to no effect and 10 corresponds to complete effect.

Responses to the items are scored to produce the following 4 domains:

- Absenteeism: work time missed due to CS = [REDACTED]
- Presenteeism: impairment while working due to CS = [REDACTED]

- Work productivity loss: overall work impairment due to CS = [REDACTED]
[REDACTED]
- Activity impairment: activity impairment due to CS = [REDACTED]

Each score is then multiplied by 100 to express domains in terms of impairment percentages, with higher numbers indicating greater impairment and less productivity (ie, worse outcomes).

3.2.6 *Carcinoid Syndrome-related Health Care Resource Utilization*

At Baseline and at each Follow-up, questionnaire items will ask patients about ER visits and hospitalizations during the prior 6-month period. Data collected will include the following:

- The number of ER visits and the CS-related reason for each visit
- The number of hospitalizations, the number of nights for each stay, and the CS-related reason for each hospitalization

3.2.7 *Study Discontinuation and Mortality*

Patients will be terminated from the study if they discontinue the use of XERMELO, withdraw consent for participation, or are lost to follow-up. Information on reasons for discontinuation will be provided by the specialty pharmacy.

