5.1.3.2 Demographics, Medical History, and Carcinoid Syndrome Treatments

Patient demographics and medical history information collected at Baseline, including prior treatments received for CS, will be summarized in separate tables. Age will be summarized both as a continuous variable and as a categorical variable (18-30 years, 31-40 years, 41-50 years, 51-64 years, 65 years or older, 75 years or older).

Information on treatments received for CS during study Follow-up, including changes in frequency and dose for short- and long-acting SSAs and additional treatments for CS ([Section 3.2.2](#)), will be summarized in tabular format for each Follow-up time point.

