5.2 Missing Data

No imputations will be performed, except as noted for the sensitivity analysis for the primary endpoint as described in Table 1 ([Section 5.1.4](#)). In all other cases, missing data will be excluded and variables will be analyzed using the available observed data.

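### The month 12–36 percentages for SSA change and weight change can rise or fall through a change in who answers, and no planned table separates this from change within patients

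*Protocol*

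**What the plan says.** **What is collected.** After month 6, Protocol Appendix A keeps the weight-change and SSA items at every survey to month 36. Protocol 8.2.1.2 says that, from month 6, "patients will be asked to describe changes (ie, frequency, dosage) in the use of short and long-acting SSA therapy, where applicable, since initiating XERMELO". SAP 3.2.1 likewise asks about weight change since starting XERMELO at each follow-up.

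**How it is summarised.** SAP 5.1.3.2 says that treatments during follow-up, including changes in SSA frequency and dose, "will be summarized in tabular format for each Follow-up time point". Weight change reaches the later tables through the questionnaire summaries for each follow-up in SAP 4.2. Protocol 10.4.1 adds, without naming either item: "For any other study endpoints assessed at 12 months and thereafter, descriptive statistics will be presented and 95% CLs will be calculated".

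**Who is counted.** SAP 5.1.1 leaves missing responses out of percentage denominators. SAP 5.2 says: "In all other cases, missing data will be excluded and variables will be analyzed using the available observed data". The only imputation is for the month-6 primary endpoint.

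**Who can answer.** Protocol 5.1.1 says: "Participation in the study is contingent on continued use of XERMELO". SAP 3.2.7 says: "Patients will be terminated from the study if they discontinue the use of XERMELO, withdraw consent for participation, or are lost to follow-up". Under Protocol 5.1, once the pharmacy reports a status change the survey link is disabled and "no further survey invitations or reminders will be triggered". Protocol 6.3 also withdraws a patient who misses one survey in a year. Protocol section 6 extends recruitment to 6 months before data collection ends, so the last patients enrolled can give only Baseline and month-6 data.

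**The concern.** A row of percentages for months 6, 12, 18, 24, 30 and 36 invites reading as a course over time. Here each percentage belongs to a different set of patients. Someone who stops XERMELO, misses a survey or enrolled late drops out of both numerator and denominator. If leaving is related to the answer, the percentage moves even when no patient's answer does.

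The fixed reference point makes this easy to misread. A patient who reported a reduction or gain at month 6 and has not changed since gives the same answer at each later survey. A shift in the mix of patients then looks the same as a shift within patients.

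At stake is the long-term description of SSA use and weight on XERMELO. SAP section 1 describes the registry as meant to collect long-term patient-reported outcomes. A reader could take growing or shrinking SSA sparing from tables that cannot show it.

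**Working it through.** **1. The plan's own figure.** SAP 2.4 assumes a proportion of 50%, a half-width of 5% and 40% dropout before month 6.

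- n = 1.96² × 0.5 × 0.5 / 0.05² = 384.2, rounded up to 385, as stated.
- N = 385 / 0.60 = 641.7, rounded up to 642, against 643 stated. The difference does not matter here.

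The documents give no retention figure after month 6 and no figure for the month 12–36 percentages.

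**2. Is a same-patient display planned?** None of the relevant sections contains one.

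- SAP 5.1.3.1 (disposition) counts leavers and reasons, but not by earlier answer.
- SAP 5.1.3.2 and 4.2 summarise each time point separately.
- SAP 5.1.4 limits imputation to the month-6 primary endpoint.
- SAP 5.1.5 covers ER visits, hospitalizations, mortality, bowel movements, subgroups and the association with satisfaction.

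**3. How far can composition alone move a percentage?** Assumptions: 385 patients answer at month 6, a share p₆ = 0.30 report a reduction (or gain), and nobody's answer changes afterwards. Retention per 6-month interval is a in reporters and b in the others. After k intervals:

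- nₖ = 385 × [p₆aᵏ + (1 − p₆)bᵏ]
- pₖ = p₆aᵏ / [p₆aᵏ + (1 − p₆)bᵏ]
- 95% CL = pₖ ± 1.96 × √[pₖ(1 − pₖ)/nₖ]

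For a = 0.85 and b = 0.75 at month 36 (k = 5), 0.85⁵ = 0.4437 and 0.75⁵ = 0.2373. The two terms are 0.30 × 0.4437 = 0.1331 and 0.70 × 0.2373 = 0.1661, which sum to 0.2992. So p = 0.1331/0.2992 = 44.5% and n = 385 × 0.2992 = 115. The same formula gives 32.7% at month 12 (k = 1) and 38.4% at month 24 (k = 3).

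| Retention, reporters / others | n at month 36 | Share at month 36 | 95% CL |
|---|---|---|---|
| 85% / 70% | 97 | 53.1% | 43.1–63.0% |
| 85% / 75% | 115 | 44.5% | 35.4–53.6% |
| 85% / 80% | 140 | 36.7% | 28.7–44.7% |
| 85% / 85% | 171 | 30.0% | 23.1–36.9% |
| 75% / 85% | 147 | 18.6% | 12.4–24.9% |

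In every row the true within-patient change is zero.

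**4. Does a paired comparison remove the effect?** Take the 85% / 75% row. Among the 115 patients still answering at month 36, the share who reported a reduction or gain at month 6 is also 44.5%, because no answer changed. The same-patient difference is 0, and this holds in every row.

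**5. Limits of the illustration.** It follows all 385 to month 36 and counts all of them for each item. Late enrolment and items asked only where applicable (rescue SSA, for example) will make n smaller. At 44.5% the interval reaches 30% once n falls to about 1.96² × 0.445 × 0.555 / 0.145² = 45. Exclusion of 30% is therefore not assured, but the shift in the point estimate does not depend on n.

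**The case against.** **The direction is not established.** A reader might infer that the percentages will rise, because Protocol 3.2 says: "The Sponsor assumes that satisfied patients will continue XERMELO to avoid the complications of CS, leading to better long-term outcomes". That sentence is about satisfaction. Nothing in the documents ties staying on XERMELO to the SSA or weight answers. Equal retention gives no movement and the reverse pattern gives a fall. This objection stands: only a possible rise or fall is supported.

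**The confidence limits may not apply.** A reader might infer that every later SSA and weight percentage will carry 95% CLs. Protocol 10.4.1 names neither item, the endpoints defined at 6-month intervals to 3 years are hospitalization, ER visits and mortality, and SAP 5.1.3.2 mentions no CLs. This stands as an open reading. The composition problem is the same with or without limits.

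**The fixed reference is not settled for SSA.** Protocol 8.2.1.2 refers to change since starting XERMELO, but the synopsis speaks of changes to previously reported data and SAP 3.2.2 gives no reference period. The fixed-answer illustration applies directly to weight, and to SSA only if Protocol 8.2.1.2 governs. The change in who answers affects both items either way.

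**There are partial safeguards.** The disposition table, the by-patient listings and the option of further analyses after data collection all exist. They let someone reconstruct the issue, but none puts a same-patient result beside the percentages.

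**The consequence is limited.** SSA reduction and weight gain are formal endpoints at month 6 only, no trend test is planned, and SAP 5.1.1 calls all analyses descriptive. This stands and limits the weight of the point, but a descriptive table can still be misread.

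**Conclusion.** The point holds in a limited form. The month 12–36 SSA-change and weight-change percentages describe whoever is still on XERMELO and responding at that survey. They can move between time points because that group changes, and no planned table separates this from change within patients.

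The size is unknown, because the documents give no retention by response. Under the assumed rates, a true constant 30% could appear at month 36 as anything from 18.6% to 53.1%. A modest gap (85% against 80%) gives 36.7% with an interval that still includes 30%.

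The documents do not support saying that the percentages will rise, or that spuriously precise intervals will certainly be attached to them. The month-6 primary and secondary results are not touched. This is an inexpensive improvement to the long-term tables, not a flaw in the main analysis.

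Separately, Protocol 6.3 does not list stopping XERMELO among its reasons for ending participation, while Protocol 5.1.1 and SAP 3.2.7 make it one. These passages need to be reconciled, since they decide who is in the later tables.

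**What to change.** In SAP 5.1.3.2 and the follow-up questionnaire summaries of SAP 4.2, for long-acting SSA dose, long-acting SSA frequency, rescue SSA and weight change at months 12–36:

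1. Beside each later proportion, print the month-6 proportion in exactly the same patients, and add a shift table from the month-6 answer to the current answer.
2. Label the all-responder proportions as describing patients still on XERMELO and responding, and state that change over time is read only from the paired rows.

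The SAP should also state the reference period of the SSA items, because the shift table is read differently if later surveys ask about change since the last report. Protocol 10.4.1 could say whether its 95% CLs cover these items.

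The cost is some SAP wording and a few extra table rows from data already collected. The possible downside is that an apparent long-term improvement shrinks once it is read in the same patients.
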